The presence of common mental health conditions at baseline will be determined for the case and control cohorts. We will examine three groups of common mental illness as defined by the International Statistical Classification of Diseases and Related Health Problems 10th Revision (ICD10) classification;²⁰ depressive episodes (F32), recurrent depressive disorder (F33), and non-phobia related anxiety disorders (F41). These conditions are chosen as they represent the most common mental health conditions presenting to primary care.²¹ These conditions will be identified using algorithms validated in UK primary care.²² We selected the algorithms used here (Appendix 2) to optimise the positive predictive value. In brief, we will use a concurrent diagnosis and treatment code to identify acute episodes (depressive episodes and anxiety episodes) and for recurrent depression either a historical code for any depression and current treatment or a recurrent

depression specific diagnosis code (Appendix 2). As a secondary analysis we will also explore the prevalence of attention deficit hyperactivity disorder (ADHD) in the case and control cohorts.

Healthcare utilisation outcomes

The components of healthcare utilisation to be examined comprise; number and duration of primary care attendances, number of primary care prescriptions for antidepressant and anxiolytic medications, number of primary care prescriptions for medications used in IBD, recorded secondary care attendances, and issue of statements of fitness for work (also termed fit notes or sick notes).

Antidepressant medication classes to be examined comprise, selective serotonin reuptake inhibitors (SSRIs) and related medications (serotonin and norepinephrine reuptake inhibitors; SNRIs), tricyclic antidepressants (TCAs) and related medications (tetracyclic antidepressant TeCAs), and monoamine oxidase inhibitors (MOAIs). Anxiolytic medications to be examined comprise all benzodiazepines and other related medications indicated for use in anxiety states (Appendix 3). Medications used for the treatment of IBD to be examined will comprise; topical 5-aminosalicylic acid (5-ASA) medications, topical glucocorticoids, oral 5-ASA medications, oral glucocorticoids, non-biologic immunosuppressant medications (cyclosporine, azathioprine, mercaptopurine, methotrexate), and biologic therapies (Appendix 3).

Other baseline measures

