XaK6C	All	Exacerbation of Crohn's disease of small intestine
J400z	All	Crohn's disease of the small bowel NOS
J401.	All	Regional enteritis of the large bowel
XE0af	All	Crohn's disease of the large bowel NOS
XaK6D	All	Exacerbation of Crohn's disease of large intestine
J40z.	All	Regional enteritis NOS
J4010	All	Crohn's colitis
J4011	All	Crohn's proctitis
X3050	All	Perianal Crohn's disease
Jyu40	All	[X]Other Crohn's disease

Supplementary table S1. Read codes used to identify inflammatory bowel disease

Appendix 2

Clinical entity	ICD 10 code	Definition
Anxiety	F41	Any coded anxiety episode AND concurrent treatment for anxiety
Depressive episode	F32	Any coded depressive episode AND concurrent treatment for depression
Recurrent depressive disorder	F33	(Any historical code* for a depressive episode AND current treatment for depression) OR Any code for recurrent depressive disorder
Anxiety treatments	NA	SSRIs, anxiolytics, counselling, CBT, and psychotherapy
Depression treatments	NA	SSRIs, TCAs, MAOIs, counselling, CBT, and psychotherapy

Supplementary table S2. Algorithms used to identify anxiety episodes, depression episodes, and recurrent major depression. Expressions in capitals equate to Boolean expressions. *More than 1 year ago. SSRIs = selective serotonin reuptake inhibitors, TCA = tricyclic antidepressants, MAOI = monoamine oxidase inhibitors, CBT = cognitive behavioural therapy.

Read V2 Code	Term ID	Description
E200.	All	Anxiety states
E2000	All	Anxiety state unspecified
E2001	All	Panic disorder
E2002	All	Generalised anxiety disorder
E2003	All	Anxiety with depression
E2004	All	Chronic anxiety
E2005	All	Recurrent anxiety
E200z	All	Anxiety state NOS
Eu41.	All	[X]Other anxiety disorders
Eu410	All	[X]Panic disorder [episodic paroxysmal anxiety]
Eu411	All	[X]Generalized anxiety disorder
Eu412	All	[X]Mixed anxiety and depressive disorder
Eu413	All	[X]Other mixed anxiety disorders
Eu41y	All	[X]Other specified anxiety disorders
Eu41z	All	[X]Anxiety disorder, unspecified
Read CTV3 Code	Term ID	Description
E200.	All	Anxiety disorder
XE1Y7	All	Panic disorder
Eu410	All	[X]Panic disorder [episodic paroxysmal anxiety]
E2002	All	Generalised anxiety disorder
X00Sb	All	Mixed anxiety and depressive disorder
X00RP	All	Organic anxiety disorder
E2004	All	Chronic anxiety
E2005	All	Recurrent anxiety
E200z	All	Anxiety state NOS
X00Sc	All	Anxiety hysteria
Eu41.	All	[X]Other anxiety disorders
Eu413	All	[X]Other mixed anxiety disorders

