Eu332	All	[X]Recurrent depressive disorder, current episode severe without psychotic symptoms
Eu333	All	[X]Recurrent depressive disorder, current episode severe with psychotic symptoms
Eu334	All	[X]Recurrent depressive disorder, currently in remission
Eu33y	All	[X]Other recurrent depressive disorders
Eu33z	All	[X]Recurrent depressive disorder, unspecified
Eu412	All	[X]Mixed anxiety and depressive disorder
Read CTV3 Code	Term ID	Description
X00Sb	All	Mixed anxiety and depressive disorder
X00SO	All	Depressive disorder
X761L	All	Seasonal affective disorder
Xa0wV	All	Recurrent brief depressive disorder
X00SQ	All	Agitated depression
XE1YC	All	Reactive depression
X00SR	All	Endogenous depression
X00SS	All	Endogenous depression first episode
XE1Y0	All	Single major depressive episode
E1120	All	Single major depressive episode, unspecified
E1120	All	Single major depressive episode, unspecified
E1121	All	Single major depressive episode, mild
E1122	All	Single major depressive episode, moderate
E1123	All	Single major depressive episode, severe, without mention of psychosis
E1124	All	Single major depressive episode, severe, with psychosis
XaX53	All	Single major depressive episode, severe, with psychosis, psychosis in remission
E1125	All	Single major depressive episode, in partial or unspecified remission
E1126	All	Single major depressive episode, in full remission
E112z	All	Single major depressive episode NOS
XM1GC	All	Endogenous depression - recurrent
E1130	All	Recurrent major depressive episodes, unspecified
E1131	All	Recurrent major depressive episodes, mild
E1132	All	Recurrent major depressive episodes, moderate
E1133	All	Recurrent major depressive episodes, severe, without mention of psychosis
E1134	All	Recurrent major depressive episodes, severe, with psychosis
E1135	All	Recurrent major depressive episodes, in partial or unspecified remission
E1136	All	Recurrent major depressive episodes, in full remission
E113z	All	Recurrent major depressive episode NOS

X00SU	All	Masked depression
E11y2	All	Atypical depressive disorder
X00S8	All	Post-schizophrenic depression
XSEGJ	All	Major depressive disorder
XSKr7	All	Cotard syndrome
XSGol	All	Moderate major depression
XSGok	All	Mild major depression
XSGom	All	Severe major depression without psychotic features
XSGon	All	Severe major depression with psychotic features
E1137	All	Recurrent depression
E130.	All	Reactive depressive psychosis
E2B..	All	Depressive disorder NEC
E2B0.	All	Postviral depression

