E2B1.	All	Chronic depression
Eu320	All	[X]Mild depressive episode
Eu321	All	[X]Moderate depressive episode
Eu331	All	[X]Recurrent depressive disorder, current episode moderate
XE1Y1	All	Recurrent major depressive episodes
XE1ZY	All	[X]Severe depressive episode without psychotic symptoms
XE1ZZ	All	[X]Severe depressive episode with psychotic symptoms
XE1Za	All	[X]Other depressive episodes
XE1Zb	All	[X]Depressive episode, unspecified
XE1Zd	All	[X]Recurrent depressive disorder, current episode severe without psychotic symptoms
XE1Ze	All	[X]Recurrent depressive disorder, current episode severe with psychotic symptoms
XE1Zf	All	[X]Recurrent depressive disorder, unspecified
XaB9J	All	Depression NOS
XaCHr	All	[X] Single episode agitated depression without psychotic symptoms
XaCHs	All	[X] Single episode major depression without psychotic symptoms
XaCIs	All	Mild depression
XaCIt	All	Moderate depression
XaCIu	All	Severe depression
E0013	All	Presenile dementia with depression
E0021	All	Senile dementia with depression

Supplementary table S4. Read codes used to identify, depression episodes.

Read V2 Code	Term ID	Description
E113.	All	Recurrent major depressive episode
E1130	All	Recurrent major depressive episodes, unspecified
E1131	All	Recurrent major depressive episodes, mild
E1132	All	Recurrent major depressive episodes, moderate
E1133	All	Recurrent major depressive episodes, severe, without mention of psychosis
E1134	All	Recurrent major depressive episodes, severe, with psychosis
E1135	All	Recurrent major depressive episodes, in partial or unspecified remission
E1136	All	Recurrent major depressive episodes, in full remission
E1137	All	Recurrent depression
E113z	All	Recurrent major depressive episode NOS
E2B1.	All	Chronic depression
Eu32A	All	[X]Recurrent major depressive episodes, severe, with psychosis, psychosis in remission
Eu33.	All	[X]Recurrent depressive disorder
Eu330	All	[X]Recurrent depressive disorder, current episode mild
Eu331	All	[X]Recurrent depressive disorder, current episode moderate
Eu332	All	[X]Recurrent depressive disorder, current episode severe without psychotic symptoms
Eu333	All	[X]Recurrent depressive disorder, current episode severe with psychotic symptoms
Eu334	All	[X]Recurrent depressive disorder, currently in remission
Eu33y	All	[X]Other recurrent depressive disorders
Eu33z	All	[X]Recurrent depressive disorder, unspecified
Read CTV3 Code	Term ID	Description
Xa0wV	All	Recurrent brief depressive disorder

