XM1GC	All	Endogenous depression - recurrent
E1130	All	Recurrent major depressive episodes, unspecified
E1131	All	Recurrent major depressive episodes, mild
E1132	All	Recurrent major depressive episodes, moderate
E1133	All	Recurrent major depressive episodes, severe, without mention of psychosis
E1134	All	Recurrent major depressive episodes, severe, with psychosis
XaX54	All	Recurrent major depressive episodes, severe, with psychosis, psychosis in remission
E1135	All	Recurrent major depressive episodes, in partial or unspecified remission
E1136	All	Recurrent major depressive episodes, in full remission
E113z	All	Recurrent major depressive episode NOS
E1137	All	Recurrent depression
E2B1.	All	Chronic depression
Eu331	All	[X]Recurrent depressive disorder, current episode moderate
XE1Y1	All	Recurrent major depressive episodes

XE1Zd	All	[X]Recurrent depressive disorder, current episode severe without psychotic symptoms
XE1Ze	All	[X]Recurrent depressive disorder, current episode severe with psychotic symptoms
XE1Zf	All	[X]Recurrent depressive disorder, unspecified

Supplementary table S5. Read codes used to identify a diagnosis of recurrent major depression.

Counselling		
Read V2 Code	Term ID	Description
67...	11	Counselling/health education
671..	All	Counselling - general
6712.	All	Counselling offered
6714.	All	Counselling carried out
6715.	All	Counselling by other agency
6716.	All	Counselling of benefit
6717.	All	Counselling of no benefit
671Z.	All	Counselling - general NOS
672..	All	Person counselled
6721.	All	Patient counselled
6722.	All	Family counselled
673..	All	Person counselled by
6731.	All	Counselled by a doctor
6732.	All	Counselled by a nurse
6733.	All	Counselled by a health visitor
6735.	All	Counselled by a social worker
6736.	All	Counselled by a counsellor
6737.	All	Counselled by a vol. worker
673Z.	All	Counselled by person NOS
8M8..	All	Counselling requested
9NJ1.	All	In-house counselling
9NJR.	All	In-house counselling first appointment
9NJT.	All	In-house counselling follow-up appointment
Read CTV3 Code	Term ID	Description
X71Ec	All	Counselling
X71Ep	All	Coping strategy counselling
XaEC1	All	Phobia counselling
XaD27	All	Family counselling
6779.	All	Psychological counselling
XaECG	All	Anxiety counselling
XaECF	All	Self-esteem counselling
XaI8j	All	Stress counselling
672..	All	Person counselled
6721.	All	Patient counselled
6722.	All	Family counselled
XE1TI	All	Person counselled by
6715.	All	Counselling by other agency
6731.	All	Counselled by a doctor

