8G101	All	Dialectical behaviour therapy
8G102	All	Behavioural parent training
8G11.	All	Psychotherapy - cognitive
8G12.	All	Psychotherapy - psychodynamic
8G120	All	Short-term psychodynamic therapy
8G121	All	Dynamic interpersonal therapy
8G122	All	Focal psychodynamic therapy
8G14.	All	Cognitive analytic therapy
8G15.	All	Computerised cognitive behavioural therapy
8G16.	All	Interpersonal psychotherapy
8G18.	All	Cognitive stimulation therapy
9NIK.	All	Seen by psychotherapist
9NIK0	All	Seen by trainee psychotherapist
8HHT.	All	Referral to psychotherapist
ZV57D	All	[V]Psychotherapy, not elsewhere classified
ZV673	All	[V]Psychotherapy or other treatment for mental disorder follow-up
8G9Z.	All	Other psychotherapy NOS
8G9..	All	Other psychotherapy
Read CTV3 Code	Term ID	Description
X71bp	All	Psychotherapy
XaaU0	All	Cognitive rehabilitation therapy
XaItc	All	Brief solution focused psychotherapy
Xa8IG	All	Psychoanalytic and psychodynamic therapy
Xa8IJ	All	Long-term exploratory psychotherapy
3841.	All	Psychoanalysis
XaA8V	All	Generic psychoanalysis
XaA8W	All	Independent psychoanalysis
XaA8T	All	Kleinian psychoanalysis
XaA8U	All	Bion-based group psychoanalysis
XaA8X	All	Classical psychoanalysis
XaA8Y	All	Lacanian psychoanalysis
XaA8g	All	Group psychoanalysis
XaA8U	All	Bion-based group psychoanalysis

384Z.	All	Psychological analysis NOS
Xa8IM	All	Jungian-based therapy
Xa8IN	All	Generic Jungian-based therapy
Xa8IP	All	Analytical psychology
Xa8IR	All	Long-term psychodynamic psychotherapy
XaA8Z	All	Developmental psychodynamic psychotherapy
XaA8c	All	Supportive expressive psychodynamic psychotherapy
XaA8d	All	Psychodynamic-interpersonal psychotherapy
XaEVq	All	Psychodynamic psychotherapy
Xad7C	All	Focal psychodynamic therapy
Xa8IR	All	Long-term psychodynamic psychotherapy
XaA8Z	All	Developmental psychodynamic psychotherapy
XaA8c	All	Supportive expressive psychodynamic psychotherapy
XaA8d	All	Psychodynamic-interpersonal psychotherapy
Xa8II	All	Short-term psychodynamic therapy
XaXuc	All	Dynamic interpersonal therapy
XaA9g	All	Specific task orientated psychotherapy
XE0iL	All	Psychotherapy/sociotherapy
8G9Z.	All	Other psychotherapy NOS
8G9..	All	Other psychotherapy

Supplementary table S6. Read codes used to identify non-medication based treatments for depression or anxiety.

Appendix 3

Medication class	Medications
Medications for mental health conditions	

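### The CTV3 lists in tables S4 and S5 have no row for four recurrent depressive disorder terms that both V2 lists hold, so some patients may be classified differently by their practice's coding system

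*Combined protocol and SAP*

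**What the plan says.** Table S2 in Appendix 2 gives two routes to F33: "Any historical code* for a depressive episode AND current treatment for depression) OR Any code for recurrent depressive disorder". The asterisk means more than one year ago. The Mental health outcomes section states the same rule: "for recurrent depression either a historical code for any depression and current treatment or a recurrent" depression code. F32 needs a depressive episode code together with concurrent treatment.

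Table S4 supplies the depressive episode codes, S5 the recurrent depression codes and S6 the non-drug treatments. Each has a Read V2 part and a CTV3 part. The section defining the IBD cohort says that both Read versions are in use in the network.

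The V2 parts of S4 and S5 both include "X]Recurrent depressive disorder, current episode mild" (Eu330) and "X]Recurrent depressive disorder, currently in remission" (Eu334), along with the parent term (Eu33.) and the other category (Eu33y). The CTV3 parts of both tables include "X]Recurrent depressive disorder, current episode severe without psychotic symptoms" (XE1Zd) and its counterpart with psychosis (XE1Ze), the moderate term (Eu331) and the unspecified term (XE1Zf). They have no row for the remaining four.

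In S6, "Interpersonal psychotherapy" has its own row in V2 (8G16.) but not in CTV3, and "Psychological counselling" (6779.) has a row in CTV3 but not in V2.

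**The concern.** The code-only route in S2, "OR Any code for recurrent depressive disorder", is only as complete as the list behind it. If a concept is listed under one Read version and absent under the other, case status depends partly on the practice's software. The stated aim of choosing algorithms with a high positive predictive value does not explain keeping a concept in one version only, and no other reason is given.

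Two results are exposed. Aim 3 reports F32 and F33 prevalence, and a coding-system difference enters those absolute figures directly. Aim 4 compares healthcare use within people with IBD, with and without a mental health condition; a missed patient joins the comparison group without one. Control matching protects neither.

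**Working it through.** The plan gives no figure on this point, so the check compares the lists and then applies the S2 rule. It assumes that each practice records in one Read version.

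**Table S5.** V2 has 20 rows and CTV3 has 18.
- Eleven codes are identical in both: E1130 to E1137 (8), E113z, E2B1. and Eu331.
- Five more pair by the same or nearly the same description: E113. with XE1Y1, Eu32A with XaX54, Eu332 with XE1Zd, Eu333 with XE1Ze, and Eu33z with XE1Zf.
- V2 rows without a counterpart: 20 − 16 = 4 (Eu33., Eu330, Eu334, Eu33y).
- CTV3 rows without a counterpart: 18 − 16 = 2 (Xa0wV, XM1GC).

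**The recurrent depressive disorder family, identical in S4 and S5:**

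| Term | V2 | CTV3 |
|---|---|---|
| Parent | Eu33. | no row |
| Mild | Eu330 | no row |
| Moderate | Eu331 | Eu331 |
| Severe, no psychosis | Eu332 | XE1Zd |
| Severe, psychosis | Eu333 | XE1Ze |
| In remission | Eu334 | no row |
| Other | Eu33y | no row |
| Unspecified | Eu33z | XE1Zf |

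**The S2 rule** for a patient whose only recurrent code is one of the four:

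| Other S4 code over 1 year old | Current treatment | F33 in V2 | F33 in CTV3 |
|---|---|---|---|
| No | No | Yes | No |
| No | Yes | Yes | No |
| Yes | No | Yes | No |
| Yes | Yes | Yes | Yes |

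Because the four terms are missing from CTV3 S4 as well as S5, they cannot serve as the historical code or as an F32 episode code. In the second row the V2 patient can also count as F32, and the CTV3 patient cannot. A patient with any other S5 code is F33 in both systems.

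**Differences in the other direction.** S4 has 52 V2 rows and 61 CTV3 rows (60 distinct, since E1120 appears twice). CTV3 S4 holds broad terms with no V2 row of that name: Depression NOS, Reactive depression, Endogenous depression and Depressive disorder. It also holds E1135 and E1136, which V2 S4 lacks although V2 S5 has them. These rows feed F32, and the broad terms also feed the treated-history route to F33, so CTV3 practices could count more patients there.

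**Table S6.** In V2 only: interpersonal psychotherapy, dialectical behaviour therapy, cognitive analytic therapy, group CBT and contact with a psychotherapist. In CTV3 only: psychological, anxiety and stress counselling, guided self-help CBT and contact with a counsellor. Treatment is required for F32, F41 and the historical route to F33.

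**The case against.** **Near-equivalents exist.** CTV3 S5 holds mild (E1131), remission (E1135, E1136) and general (E1137, XE1Y1) recurrent major depression codes, besides the unspecified term XE1Zf. Any of them makes the patient F33. This stands, and it narrows the group at risk. It does not remove the gap: V2 S5 lists both families, and CTV3 lists both for moderate and severe disease.

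**The dictionary is not in the documents.** They do not show that CTV3 has separate codes for the four terms, or which code a CTV3 practice would use. Printed descriptions are an imperfect guide: J40z. and E200. carry different descriptions in the two versions, and rows marked All under Term ID may cover terms not printed. This also stands. An oversight is plausible, not proven.

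**Practice matching protects the contrast.** The Abstract promises matching on practice, which would put cases and controls under the same coding system and make the loss largely non-differential. The section defining the matched cohort guarantees only age and gender, and Aim 3 also names only those two. So the protection is likely but not assured.

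**S6 matters little.** SSRIs alone satisfy the treatment requirement for either condition, TCAs or MAOIs do so for depression, and both versions hold general counselling and psychotherapy codes. That limits the effect of S6, though it does not justify the differences.

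**A numerical reading.** A reader might assume a CTV3 share c of 20–40% and a share m of 10–30% of code-route F33 patients who hold only an omitted term. That gives an under-count c × m from 0.20 × 0.10 = 2% to 0.40 × 0.30 = 12%, and a V2-to-CTV3 ratio 1/(1 − m) from 1.11 to 1.43. These are not estimates. Neither input is in the documents, and the formulas ignore the two CTV3-only codes in S5 and recovery through treated history.

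**Conclusion.** The concern holds in a limited form. As printed, the lists can classify identical patients differently by Read version. The clearest case is a patient whose only depression code is one of the four terms: F33 in a V2 practice, possibly missed in a CTV3 practice. Patients with another listed recurrent code, or with another historical depression code plus current treatment, are unaffected.

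A reader might infer that CTV3 practices capture no mild or in-remission recurrent depression, or that F33 is under-counted overall. The documents support neither: the parallel family is listed, and the differences run both ways.

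The size is 4 of 20 V2 rows in S5 without a CTV3 counterpart, against 2 of 18 the other way. The number of patients and the net direction cannot be computed, because no code counts or CTV3 practice share are given. The conclusion rests on matching rows by code or printed description and on extraction following the printed rows. The effect falls on absolute prevalence (Aim 3) and the within-IBD split (Aim 4); it reaches the IBD-control contrast mainly if practice matching is not applied.

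**What to change.** Before extraction:

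1. Cross-map S4, S5 and S6 concept by concept against both Read dictionaries.
2. Add the CTV3 equivalents of Eu33., Eu330, Eu334 and Eu33y to S4 and S5 where they exist. Where none exists, say so and name the listed CTV3 code that carries the concept. Do not drop V2 codes by default: if CTV3 holds the concept under a listed code, dropping it would create a new mismatch.
3. Add E1135 and E1136 to V2 S4 or explain their omission, and settle whether the broad CTV3 terms in S4 have V2 equivalents.
4. Align the therapy codes in S6 in the same way.
5. State in the matched-cohort section whether practice is a matching factor.
6. After extraction, tabulate F32, F33 and F41 prevalence by Read version, separately for IBD and controls, as a check.

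The cost is a few hours of code-list work, an appendix edit and one extra table. No new data are needed.

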SSRIs and related medication	Venlafaxine, Bupropion, Duloxetine, Naltrexone, Citalopram, Dapoxetine, Escitalopram, Fluoxetine, Fluvoxamine, Paroxetine, Sertraline
TCA's	Amitriptyline, Clomipramine, Dosulepin, Doxepin, Mianserin, Trazodone, Trimipramine, Imipramine, Lofepamine, Nortriptyline
MAOIs	Tranlycypromine, Phenelzine, Isocarboxazid, Moclobemide
Anxiolytic medications	Alprazolam, Chlordiazepoxide, Clobazam, Clonazepam, Diazepam, Lorazepam, Oxazepam, Buspirone, Meprobamate, Clomipramine, Clomethiazole
Medication for IBD	
Topical 5-ASA	Mesalazine, Sulfasalazine
Topical glucocorticoids	Budesonide, Hydrocortisone, Prednisolone
Oral 5-ASA	Balsalazide, Mesalazine, Olsalazine, Sulfasalazine
Oral glucocorticoids	Prednisolone, Cortisone, Dexamethasone, Methylprednisolone, Beclomethasone, Betamethasone, Budesonide, Deflazacort
Antimetabolites	Azathioprine, Mercaptopurine, Methotrexate
Biologic therapies	Adalimumab, Golimumab, Infliximab, Vedolizumab

Supplementary table S7. Medications analysed by medication class. SSRI = selective serotonin reuptake inhibitors, TCA = tricyclic antidepressants, MAOI = monoamine oxidase inhibitors, 5ASA = 5-aminosalicylic acid.

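### Supplementary table S7 does not match the antidepressant groups defined in Methods, gives no counting rule for clomipramine, and is not tied to the class names in table S2

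*Combined protocol and SAP*

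**What the plan says.** Methods, Healthcare utilisation outcomes, names three antidepressant groups. The first is "selective serotonin reuptake inhibitors (SSRIs) and related medications (serotonin and norepinephrine reuptake inhibitors; SNRIs", so the related drugs are SNRIs. The second is "tricyclic antidepressants (TCAs) and related medications (tetracyclic antidepressant TeCAs", so tetracyclics belong to the tricyclic group. The third is the MAOIs. For anxiolytics it says: "Anxiolytic medications to be examined comprise all benzodiazepines and other related medications indicated for use in anxiety states (Appendix 3".

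Appendix 3, Supplementary table S7, is captioned as the list of drugs analysed by class, and no other table lists drugs. Its relevant rows are:

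- SSRIs and related: the row begins "Venlafaxine, Bupropion, Duloxetine, Naltrexone, Citalopram, Dapoxetine" and continues with five more drugs.
- TCAs, labelled without any mention of related drugs: the row begins "Amitriptyline, Clomipramine, Dosulepin, Doxepin, Mianserin, Trazodone". Mirtazapine is not in it or anywhere else in the table.
- Anxiolytics: the row ends "Buspirone, Meprobamate, Clomipramine, Clomethiazole".

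Appendix 2, Supplementary table S2, defines depression treatment as "SSRIs, TCAs, MAOIs, counselling, CBT, and psychotherapy". Its anxiety treatments are SSRIs, anxiolytics and the same three non-drug therapies; TCAs are not among them. S2 does not cite S7.

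**The concern.** S7 serves two purposes. It determines which prescriptions count towards a named utilisation outcome, which Statistical Analyses says will be reported as event rates. It is also the only possible source of drugs for the treatment condition in S2, because table S6 covers non-drug treatment only.

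A wrong list therefore gives wrong absolute prescription rates. It can also change who meets a mental health definition. That affects the prevalence description in Aim 3 and the split of people with IBD into those with and without mental health problems in Aim 4.

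**Working it through.** The plan gives no prescription volumes and no sample size, so there is no figure to reproduce. The check compares the lists and then traces the consequences.

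**1. Count of entries.** The four mental-health rows of S7 hold 11 (SSRIs and related) + 10 (TCAs) + 4 (MAOIs) + 11 (anxiolytics) = 36 entries for 35 distinct drugs. The one duplicate is clomipramine, listed as a TCA and as an anxiolytic.

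**2. Rows against Methods.** The documents do not classify individual drugs, so this step uses general pharmacology.

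- SSRI row: bupropion and naltrexone are neither SSRIs nor SNRIs. Bupropion is an antidepressant, so it is in the wrong group. Naltrexone is an opioid antagonist and does not belong in an antidepressant count.
- TCA row: mianserin, a tetracyclic, is where Methods puts it. Mirtazapine, also a tetracyclic, is missing. The row label omits the related drugs.

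**3. Absolute prescription rates.** If a share m of true antidepressant prescriptions is omitted, the recorded rate is (1 − m) × the true rate. For an assumed m of 5% to 20%, that is 0.95 to 0.80 of the true rate. A wrongly included share e gives (1 + e) × the true rate.

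**4. IBD-control rate ratio.** With subscript 1 for IBD and 0 for controls, the recorded ratio is the true ratio times (1 − m1)/(1 − m0) for omission, or (1 + e1)/(1 + e0) for wrong inclusion. All shares below are assumptions.

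| Error | IBD | Control | Factor |
|---|---|---|---|
| Omission | 10% | 10% | 0.90/0.90 = 1.000 |
| Omission | 12% | 10% | 0.88/0.90 = 0.978 |
| Omission | 15% | 10% | 0.85/0.90 = 0.944 |
| Omission | 20% | 10% | 0.80/0.90 = 0.889 |
| Wrong inclusion | 2% | 1% | 1.02/1.01 = 1.010 |
| Wrong inclusion | 1% | 3% | 1.01/1.03 = 0.981 |

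**5. Clomipramine.** If antidepressant and anxiolytic counts are added together, each clomipramine prescription is counted twice. If they are reported separately, each count is correct for its own list, but the two overlap.

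**6. S2 under its two possible readings.** Each entry assumes that the required diagnosis code is present and that the drug is the only recorded treatment.

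| Drug | S2 names mean the S7 rows | S2 names read literally |
|---|---|---|
| Naltrexone, bupropion | Meet the depression and anxiety treatment conditions | Meet neither |
| Venlafaxine, duloxetine (SNRIs) | Meet both | Meet neither |
| Mianserin | Meets the depression condition | Does not |
| Mirtazapine | Meets neither | Meets neither |

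The two readings give different cases, and mirtazapine fails under both. Clomipramine can satisfy the anxiety condition through the anxiolytic row although S2 leaves TCAs out of that condition.

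**The case against.** Several stronger readings are tempting, and the documents do not support them.

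- *A reader might infer that S7 lacks a tetracyclic class that Methods promised.* Methods promises a combined tricyclic and tetracyclic group, and mianserin sits in it. A separate tetracyclic row would create a new mismatch.
- *A reader might infer that clomipramine is certainly counted twice.* Nothing says class totals will be summed, and S2's conditions are Boolean, so no patient is counted twice. Methods defines anxiolytics by indication and by reference to Appendix 3, so the second listing may be deliberate. A counting rule is enough.
- *A reader might infer that naltrexone alone can create a case.* Every S2 definition needs a diagnosis code, and naltrexone counts only if S2's SSRIs means the whole S7 row. One cannot take that reading and also read TCAs literally in order to say that mianserin is excluded.
- *A reader might infer that the IBD-control comparison is biased.* That requires unequal shares, and the documents give no reason to expect them.

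The effect on case status is also limited. Counselling, CBT or psychotherapy satisfies the treatment condition, and recurrent depressive disorder can be met by a code alone. Methods says the algorithms were validated and chosen for positive predictive value, so some loss of sensitivity was accepted, and any change to S2 may depart from what was validated.

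What stands is that the lists and the definitions disagree, and that S2's class names are undefined at drug level. Equal omission protects the ratio but not an absolute rate or a prevalence, and the plan sets out to report both.

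**Conclusion.** The point holds as a minor specification error. Followed as written, S7 includes one drug that is not an antidepressant, puts another in a group whose definition it does not meet, omits mirtazapine although Methods says tetracyclics will be examined, and leaves the counting of clomipramine open.

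Absolute prescription rates are misstated by the omitted or wrongly included share. That share is unknown, and the 5-20% range is an illustration. Some people with a depression code will fail the depressive-episode definition, namely those whose only recorded treatment is an omitted drug; their number cannot be derived from the documents. The between-cohort ratio is affected only if the share differs between cohorts.

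The conclusion assumes that S7 is the extraction list, as its caption indicates, and relies on general pharmacology for the class of each drug.

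**What to change.** Before extraction:

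1. In S7, relabel the tricyclic row as TCAs and related (tetracyclics), keep mianserin there and add mirtazapine.
2. Remove naltrexone. Either remove bupropion from the SSRI/SNRI row or report it under a separate heading for other antidepressants.
3. State that each clomipramine prescription counts once in any combined total. Also state whether it qualifies as anxiety treatment, given that S2 leaves TCAs out of that condition.
4. In S2, state that the drug-class names mean the corrected S7 rows, and note any departure from the validated algorithm.

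The cost is a small code-list edit, recorded as an amendment if the protocol is already registered, and possibly a minor departure from the validated algorithm. The effect of that departure cannot be judged from the documents.
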